2.6.3 Pharmacokinetic endpoints

Pharmacokinetics of the study drugs will be assessed to support a secondary objective using the PK datasets and will be reported by treatment groups following the general analysis conventions used for the safety set (see [Section 2.1](#)).

PK parameters

PK parameters such as those listed in [Table 2-6](#) will be estimated and reported, when applicable. The PK parameters are derived based on non-compartmental methods for NIR178 and its metabolite NJI765 and PDR001.

Table 2-6 Non-compartmental PK parameters

AUCinf	The AUC from time zero to infinity (ng*hr*mL-1)
AUClast	The AUC from time zero to the last measurable plasma concentration sampling time (tlast) (ng*hr*mL-1)
AUCtau	The AUC calculated to the end of a dosing interval (tau) at steady-state (amount x time x volume-1)
Cmax	The maximum (peak) observed plasma concentration following a single dose administration (ng/mL)
Tmax	The time to reach maximum (peak) plasma concentration following a single dose administration (hr)
T1/2	The elimination half-life associated with the terminal slope (λ_z) of a semi logarithmic concentration-time curve (hr).
¹ CL/F	The total apparent body clearance of drug (L*hr-1)
¹ Vz/F	The apparent volume of distribution during terminal phase (associated with λ_z) (L)

¹ For parent drug only

Descriptive statistics (n, arithmetic mean, CV% mean, standard deviation (SD), median, geometric mean, CV% geo-mean, minimum, and maximum) will be presented by treatment groups using the

PAS for all PK parameters defined in [Table 2-6](#) except Tmax, where only n, median, minimum, and maximum will be presented.

For NJI765, CL/F, Vz/F and elimination half-life will not be reported.

PK parameters estimated for the Japanese patients in Japanese safety run-in study may be reported consolidatively with rest of the Phase II study patients.

All individual PK parameters will be listed by treatment using the safety set.

PK concentrations

Descriptive statistics (n, m (number of non-zero concentrations), arithmetic mean, CV% mean, SD, median, geometric mean, CV% geo-mean, minimum, and maximum) for NIR178, NJI765, and PDR001 concentration will be presented at each scheduled timepoint by treatment using the PAS.

Individual concentration-time profiles for NIR178, NJI765, and PDR001 concentrations with median will be displayed graphically by treatment using the safety set on the semi-log view. In addition, the mean (+/- SD) concentration-time profiles for NIR178, NJI765, and PDR001 by treatment over time will be displayed graphically using the PAS on the linear and semi-log view.

PK plasma concentration time profiles of Japanese patients in Japanese safety run-in study will be reported separately from Phase II study patients.

All individual plasma NIR178, NJI765, and PDR001 concentration data will be listed by treatment using the safety set.

Handling of PK data below LLOQ or missing

All concentration values below the lower limit of quantitation (LLOQ) are set to zero by the Bioanalyst and will be displayed in the listings as zero and flagged. LLOQ values will be treated as zero in any calculations of summary statistics and treated as missing for the calculation of the geometric means and their CV%. The number of non-zero concentrations will also be reported in the summary statistics.

Missing values for any PK data will not be imputed and will be treated as missing.

At the time of analysis, concentration data from patients may be removed from the estimation of certain PK parameters depending on the number of available blood samples, concomitant medications, vomiting, etc. Reason(s) for removing concentration data will be provided. Specific timepoints might be removed from the analysis set if technical issues with the sample are reported (e.g., sampling issues, missing information). These patients and concentration data points will be identified at the time of analysis.

2.6.4 PD and PK/PD analyses

Not applicable.

2.6.5 Immunogenicity

Immunogenicity of PDR001 will be assessed to support a secondary objective using the IG datasets and will be reported by treatment groups following the general analysis conventions used for the safety set (see [Section 2.1](#)).

2.6.5.1 Sample ADA status

Each anti-drug anti-body (ADA) sample is assessed in a three tiered anti-drug anti-body (ADA) testing approach. All ADA samples are analyzed in the initial screening assay (first tier). Samples testing negative in the screening assay are not patient to a confirmatory assay. Samples testing positive in the screening assay are then patiented to the confirmatory assay to demonstrate that ADA are specific for the therapeutic protein product (second tier). The titer of confirmatory positive samples will be subsequently determined in the titration assay (third tier).

Samples identified as positive in the confirmatory assay are considered ADA positive.

Samples can test negative in either the screening or confirmatory assay but for analysis purposes they are not differentiated. The following properties of each sample will be provided in the source data:

- Result of assay according to pre-specified confirmatory cut point: 'POSITIVE', 'NEGATIVE', or 'NOT REPORTABLE'
- Titer: numerical representation of the magnitude of ADA response
- Threshold for determining treatment-boosted (titer fold change (i.e. x-fold))

The following definitions apply only to non-missing samples:

- ADA-negative sample: Sample where assay result is 'NEGATIVE'
- ADA-positive sample: Sample where assay result is ADA positive.

The following definitions apply only to post-baseline ADA-positive samples with a corresponding non-missing baseline sample. To be classified as treatment-boosted or treatment-unaffected, both the post-baseline and baseline titer must be non-missing:

- *treatment-induced ADA-positive sample*: ADA-positive sample post-baseline with ADA-negative sample at baseline.
- *treatment-boosted ADA-positive sample*: ADA-positive sample post-baseline with titer that is at least the titer fold (i.e. x-fold) change greater than the ADA-positive baseline titer.
- *treatment-unaffected ADA-positive sample*: ADA-positive sample post-baseline with titer that is less than the titer fold (i.e. x-fold) change greater than the ADA-positive baseline titer.

The following summaries of ADA sample status (n and %) will be provided using Immunogenicity prevalence set specific to a study drug:

- ADA-positive samples (i.e. ADA prevalence), both overall and by time point (including baseline). For summaries by time point, the denominator is the number of patients at that time point with a non-missing sample.

Listings will be provided of ADA sample status specific to the PDR001 component of the study treatment.

2.6.5.2 Patients ADA status

Any ADA sample collected after extended follow up period of 150 days of the last dose of the drug spartalizumab will not be used for summaries or derivations and will only be included in the listing.

Patient ADA status is defined as follows:

- *Treatment-induced ADA-positive patient*: patient with ADA-negative sample at baseline and at least one treatment-induced ADA-positive sample.
- *Treatment-boosted ADA-positive patient*: patient with ADA-positive sample at baseline and at least one treatment-boosted ADA-positive sample.
- *Treatment-unaffected ADA-positive patient*: patient with ADA-positive sample at baseline, no treatment-boosted ADA-positive samples, and at least one treatment-unaffected ADA-positive sample.
- *Treatment-reduced ADA-positive patient*: patient with ADA-positive sample at baseline and at least one non-missing post-baseline sample, all of which are ADA-negative samples.
- *ADA-negative patient*: patient with ADA-negative sample at baseline and at least one non-missing post-baseline sample, all of which are ADA-negative samples.
- *Inconclusive patient*: patient who does not qualify for any of the above definitions or a patient for which the baseline sample is missing.

The following summaries of ADA patient status (n and %) will be provided using Immunogenicity incidence set (for % the denominator is the number of patients in the Immunogenicity incidence set unless otherwise specified):

[figure not shown]
- Patients with ADA-negative sample at baseline
- Patients with ADA-positive sample at baseline
- ADA-negative patients: for %, the denominator is the number of patients in Immunogenicity incidence set.
- Treatment-induced ADA-positive patients; for %, the denominator is the number of patients with ADA-negative sample at baseline.
- Treatment-boosted ADA-positive patients; for %, the denominator is the number of patients with ADA-positive sample at baseline.
- Treatment-reduced ADA-positive patients; for %, the denominator is the number of patients with ADA-positive sample at baseline.

- ADA-positive patients (i.e. ADA incidence): calculated as the number of treatment-induced, treatment-boosted and treatment-reduced ADA-positive patients; for %, the denominator is the number of patients in Immunogenicity incidence set.

Listings will be provided of ADA patient status.

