Amendment of the safety run-in to assess NIR178 240mg BID in combination with PDR001 400mg Q4W starting at Cycle 1 in Japanese patients. No obvious ethnic differences in safety and PK were observed between Japanese versus non-Japanese patients and no DDI between NIR178 and PDR001 was observed. Therefore, patients in the Japanese safety run-in will receive this investigational combination therapy starting at Cycle 1.

Revision in the definition of end of study to include the option for patients on study treatment and who, in the opinion of the investigator, are still deriving clinical benefit at the time of end of study, to transfer to another study or to an alternative treatment option to continue providing study treatment to these patients.

Addition of potential drug-induced liver injury (DILI) follow-up guidance based on a Health Authority request. Further recommendations for dose reduction and follow up for DILI and pneumonitis have been added. To date, no Hy's law cases or death cases due to hepatic adverse events have been reported.

Study Status

As of August 3rd, 2020 a total of 266 patients were treated in the study. In Part 1, 198 patients were treated: RCC, mCRPC, TNBC, DLBCL, HNSCC, Melanoma, MSS Colorectal Cancer, Pancreatic, Urothelial. In Part 2, 62 NSCLC patients were treated: Schedule 1 (22), Schedule 2 (20) and Schedule 3 (20). Part 2 of the study is now closed to enrollment. In the Japanese safety run-in, 6 patients were treated: NIR178 single agent 80mg (3) and NIR178 single agent 160mg (3) during Cycle 1.

Changes in the protocol

Changes to specific sections of the protocol are shown in the track changes version of the protocol using strike through red font for deletions and red underlined for insertions:

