The following rules will be followed for reporting results unless stated otherwise:

- Part 1: In general, all TFLs will be presented by *treatment indications* unless specified otherwise.

- Disposition, demographics and baseline characteristics: Treatment groups at the most granular levels of treatment indication will be used for reporting on disposition, analysis sets, demographics, disease history, prior treatment and other baseline characteristics. If in the given programming environment, presentation of summaries on all the treatment groups is visually constraining, then these summaries may be presented separately for safety and efficacy using their respective consolidated treatment groupings as defined below.
- Safety/PK/IG: Treatment groups at the dose level of any treatment indication consolidating the categories of indication (consolidated by tumor types with no sub-grouping) will be used for reporting on safety and related endpoints like PK/IG.

█ [REDACTED]

- Part 2: All TFLs will be presented by the treatment dosing schedule.
- Part 3: If done, the presentation of TFLs will be similar to Part 1; however, if the indications selected from Part 1 do not have categories, then the Part 3 summaries may be consolidated with Part 2 for condensed CSR reporting.

Japanese safety run-in study

The data from this study is planned to be reported in the CSR separately from the Phase II study regardless of the Japanese patients' participation in the latter. However, for the brevity of CSR reporting, if deemed necessary, its reporting may be consolidated with safety reporting of Part 2. The efficacy data from this cohort will not be summarized but only listed.

Note: In a scenario that the results from part2, part 3 or the Japanese safety run-in are presented consolidatively and sorting on output data is involved for better interpretation of the results (e.g., AE summaries), then the results will be presented by study parts (part2, part 3, Japanese safety run-in) within the same output to have their own independent sorting.

Qualitative data (e.g., gender, race, etc.) will be summarized by means of contingency tables (frequencies and percentages) by treatment group; a missing category will be included as applicable. Percentages will be calculated using the number of patients in the relevant population or subgroup as the denominator.

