2.2.4 Immunogenicity analysis set

The immunogenicity (IG) set includes two parts: IG prevalence set and IG incidence set:

- The IG prevalence set includes all patients in the Safety set with a non-missing baseline ADA sample or at least one non-missing post-baseline ADA sample.
- The IG incidence set includes all patients in the Immunogenicity prevalence set with a non-missing baseline ADA sample and at least one non-missing post-baseline ADA sample.

Note that the two datasets are specific to a study drug (in this study, only PDR001) with ADA sample drawn to detect monoclonal antibodies specific to that drug.

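### The SAP's ADA incidence row counts patients who were ADA-positive only at baseline, so it exceeds induced plus boosted by (treatment-reduced)/N

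*SAP*

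**What the plan says.** Immunogenicity of PDR001 is a secondary objective (SAP Table 1-1). SAP Section 2.2.4 defines two analysis sets. The prevalence set takes patients with a baseline or a post-baseline ADA sample. The incidence set is narrower and "includes all patients in the Immunogenicity prevalence set with a non-missing baseline ADA sample and at least one non-missing post-baseline ADA sample".

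Section 2.6.5.1 works at sample level. It introduces the induced, boosted and unaffected classes with "The following definitions apply only to post-baseline ADA-positive samples with a corresponding non-missing baseline sample". Its summary on the prevalence set is "ADA-positive samples (i.e. ADA prevalence), both overall and by time point (including baseline").

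Section 2.6.5.2 works at patient level. It defines treatment-reduced as a "patient with ADA-positive sample at baseline and at least one non-missing post-baseline sample, all of which are ADA-negative samples". The table for the incidence set then has rows for baseline-negative, baseline-positive, ADA-negative, induced, boosted and reduced patients. Its last row is called ADA-positive patients, glossed as ADA incidence, and is "calculated as the number of treatment-induced, treatment-boosted and treatment-reduced ADA-positive patients". The denominator is the incidence set. Treatment-unaffected patients are defined but have no row and are not in the total.

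**The concern.** A patient who enters with ADA and never tests positive again has not acquired ADA on treatment, yet the row counts that patient as incident. Antibody present at baseline is already reported twice elsewhere: in the prevalence summary and in the row for baseline-positive patients. Requiring both a baseline and a post-baseline sample for the incidence set makes sense if incidence measures change on treatment. On that footing only induced and boosted patients belong in the numerator.

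As written, the study could report a non-zero ADA incidence for a stated secondary objective when no patient developed or boosted ADA. Adding the printed induced and boosted percentages does not reveal this, because they use baseline-negative and baseline-positive denominators respectively, not N. A reader would have to go back to the counts.

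**Working it through.** **Notation.** I = induced, B = boosted, R = reduced, U = unaffected patients; N = Immunogenicity incidence set. The SAP is a plan and gives none of these counts, so there is no stated figure to reproduce.

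**Step 1: who has a positive sample after baseline.** I classified every combination of baseline status (negative, positive) and three post-baseline samples (negative, positive below the titer-fold threshold, positive at or above it), with all titers available. That is 2 × 27 = 54 patterns.

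| Patient status | Patterns | Any post-baseline positive? |
|---|---|---|
| Induced | 26 | always |
| Boosted | 19 | always |
| Unaffected | 7 | always |
| Reduced | 1 | never |
| ADA-negative | 1 | never |

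Reduced patients stand with the ADA-negative patients on this test. The row includes them and omits the unaffected.

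**Step 2: compare the row with each plain meaning it could have.** Inconclusive patients are ignored.

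| Meaning | Formula | SAP row minus this |
|---|---|---|
| New or boosted on treatment | (I+B)/N | R/N |
| Any post-baseline positive | (I+B+U)/N | (R−U)/N, either sign |
| Ever positive | (I+B+R+U)/N | −U/N |

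The SAP row, (I+B+R)/N, matches none of them in general. The first difference is an identity: (I+B+R)/N − (I+B)/N = R/N.

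**Step 3: edge case on assumed counts.** With I = 0, B = 0, R = 1, N = 20, the SAP row is 1/20 = 5.0%, while induced plus boosted is 0%.

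**Step 4: effect of one reduced patient in the real reporting groups.** Part 2 is reported by dosing schedule (SAP Section 2.1). Part 1 immunogenicity uses dose-level groups "consolidated by tumor types with no sub-grouping) will be used for reporting on safety and related endpoints like PK/IG".

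| Group | Count and source | One reduced patient adds |
|---|---|---|
| Part 2, Schedule 1 | 22 treated (Protocol Amendment 06, Study Status) | 1/22 = 4.5 points or more |
| Part 2, Schedules 2 and 3 | 20 treated each (same place) | 1/20 = 5.0 points or more |
| Pancreatic; urothelial | 14 enrolled each (Amendment 05, Study Status); both stopped (Protocol 14.4.5) | 1/14 = 7.1 points or more |
| MSS CRC | 58 enrolled (Amendment 05, Study Status) | 1/58 = 1.7 points, approximate |

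The Part 2 and 14-patient values are minimums, because the incidence set cannot exceed the patients treated or enrolled. The 58 is an enrolled count that may have grown later.

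**Step 5: illustration with assumed rates.** Suppose 5% of patients are baseline-positive, half of those are reduced and 10% of them boosted, and 5% of baseline-negative patients are induced. Then I = 0.95 × 5% = 4.75%, B = 0.5% and R = 2.5% of N. The SAP row is 7.75%, against 5.25% for induced plus boosted, an excess of 2.5 points. Varying baseline positivity over 2% to 10% and the reduced share over 25% to 75% moves the excess from 0.5 to 7.5 points. None of these rates comes from the documents.

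**The case against.** The strongest reply is that the definition is explicit and may be deliberate. Neither document defines ADA incidence as induced plus boosted, so calling the row too high measures it against a definition brought from outside. The SAP change history says the immunogenicity analysis in Section 2.6.5 was brought into line with an immunogenicity protocol that is not available here, and that source may specify this formula. Prevalence and incidence also differ in unit (sample or patient) and in population, so the contrast between them does not by itself settle what incidence must exclude. Finally, the row could be read as a total of the three treatment-classified ADA-positive rows, with only the incidence gloss being loose.

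Much of this stands as a limit. The intent is unknown, and leaving out unaffected patients is right only under the induced-plus-boosted reading. The row is one descriptive line, and induced plus boosted can be rebuilt by adding two printed counts and dividing by N. The point-per-patient figures are reciprocals of treated or enrolled counts, and the real excess may be zero.

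It does not rescue the row. The total-of-classes reading fails because unaffected patients carry the same ADA-positive name and are missing. No reading makes a patient who lost ADA an incident case. A source that cannot be seen gives no reason, and neither document states one. If the inclusion was intended, the label would still be wrong.

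**Conclusion.** The concern holds. By the SAP's own definitions, the ADA incidence row contains patients with no positive sample after treatment starts. Taking incidence as ADA that is new or boosted on treatment, the overstatement is exactly R/N: zero with no reduced patients, and otherwise about 5 points per reduced patient in a Part 2 group. If the row was meant to count anyone positive after baseline, the error is (R−U)/N and could go either way, but reduced patients still would not belong. The actual size cannot be computed without ADA counts. No hypothesis, decision rule, sample size or power depends on the row. The correction should be made because the figure would be published as a rate for a secondary objective.

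**What to change.** Define ADA incidence in SAP Section 2.6.5.2 as (treatment-induced + treatment-boosted) divided by the Immunogenicity incidence set. Keep treatment-reduced only in its existing row with the baseline-positive denominator. Remove or change the ADA-positive label on the incidence row. When making the edit, check the row against the immunogenicity protocol cited in the change history. If that source requires the current total, report it under another name and state the reason. Optionally, add rows for treatment-unaffected and inconclusive patients so that the statuses sum to N.

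The cost is one definition and one row label, with matching updates to the TFL shells and the Programming Datasets Specifications. SAP Section 1 provides the route: an amendment before database lock or an addendum after it. No new data are needed and no other analysis changes.

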2.6.6 Patient-reported outcomes

Not applicable.

2.8 Interim analysis

Part 1:

Patients will be continuously accrued and the data will be analyzed using a Bayesian hierarchical model mentioned in [Section 2.5.2](#). Interim analysis for a treatment indication will be performed when at least 10 enrolled patients have at least one post-baseline disease assessment. Note: As of Protocol Amendment 6, the groups, RCC IO naïve (NIR178 240 mg BID) and MSS-CRC, were extension of the earlier cohorts - the former had new patients enrolled at 240 mg as a result of Protocol Amendment 5; and, the latter was split in two groups, RAS wild type and RAS mutant, with 20 patients each upon decision to expand enrollment at their respective IA.

The futility analysis will not be binding. At each of these analyses, the current (posterior) probability that the response rate for each of the treatment indications is greater than “clinically meaningful threshold (column for C2 in [Table 2-4](#))” will be determined.

These probabilities will be used to adapt the design. All available data for evaluable patients will be used for analysis at each interim analysis. However, a decision will be made only for the qualified treatment indication (≥ 10 patients with at least one post-baseline assessment) based on the calculated probability as given below:

1. Accrual to a treatment indication will cease for futility if it is very unlikely (posterior probability $< 20\%$) that the response rate for the treatment indication is “clinically meaningful” (\geq C2 threshold in [Table 2-4](#))
2. Otherwise, recruitment will continue until the next IA is performed or a maximum of 30 patients in that treatment indication has been enrolled.

For the purpose of the IA, if a patient is still on study and the last available efficacy assessment is a PR/CR which is yet to be confirmed by a subsequent scan, then this patient will be considered as a responder.

The results at the final analysis within a treatment indication will be regarded as positive if the posterior mean ORR is greater than the threshold for clinically relevant activity and the posterior probability of not being clinically meaningful is low (less than 10%).

Depending on enrollment, there may be multiple interim analyses.

Japanese safety run-in study:

No formal interim analyses are planned. However, the dose-escalation design for safety run-in part foresees that decisions based on the current data are taken before the end of the planned safety run-in part. Details of this procedure and the process for communication with Investigators are provided in [Section 1.1.4](#).

3 Sample size calculation

3.1 Part 1

The design of this part is adaptive in nature; hence, the final sample size is not fixed. As of Protocol Amendment 6, a minimum of 10 and a maximum of 30 evaluable patients will have enrollment in 13 treatment indication groups (see [Section 2.5.2.1](#)). Thus, the total sample size across all treatment indications will be between 130 and 310.

Patients will be continuously accrued, and the accumulated data will be analyzed at interim as described in [Section 2.8](#). Based upon the results of any of these analyses, enrollment into one or more treatment indications may be terminated.

The operating characteristics for this Bayesian Design are evaluated using simulation. Simulation-based probability estimates (relative frequencies) of futility at interim and positive results at final analysis for each tumor type in four scenarios (see Protocol Table 14-12) are provided in Protocol Appendix 4. The number of simulations generated for each scenario is 1000. For additional details, please see Protocol Appendix 4. Presented below is a summary of the operating characteristics based on eight tumor types included in the initial protocol design prior to interim analysis:

Protocol Table 14-13 (Scenario 1) presents the operating characteristics of the design when the true underlying ORR of none of the eight tumor types is clinically meaningful (in other words, null case for all tumor types). The false positive rate (for final analysis) for each tumor type is appropriately controlled, ranging between 2.6% and 6.8%. Similarly, the chances of stopping for futility at IA are high, ranging from 45.8% to 69.7%.

Protocol Table 14-14 (Scenarios 2a and 2b):

- Scenario 2a presents the operating characteristics when the true underlying ORR of all the eight tumor types is clinically meaningful (in other words, alternative case for all tumor types). The probability of positive conclusion (at final analysis) for each tumor type is appropriately high, ranging between 78.2% and 90.7%. Similarly, the chances of stopping for futility at IA is low, ranging between 3% and 11.9%.
- Scenario 2b, in contrast to Scenario 2a, presents the case where, out of all eight tumor types there is one single tumor type (T4-Bladder) which does not have clinically meaningful ORR while all other seven tumor types have clinically meaningful ORR. However, the model adapts appropriately and the false positive rate (1.1%) for T4 is effectively controlled. For the rest seven tumor types which have clinically meaningful ORR (same as Scenario 2a), the probability of positive conclusion has slightly changed (vs Scenario 2a) but remained acceptably high (ranging between 79.6% and 88.7%).

Protocol Table 14-15 (Scenario 3) presents the operating characteristics when four tumor types have clinically meaningful ORR while the other four do not have clinically meaningful ORR. In this scenario as well, the false positive rates for the inactive tumor types are properly controlled (4.9% - 6.9%) while the probability of positive conclusion for the active tumor types are high (78.2% - 86.6%).

Note:

Simulations were run after the inclusion of MSS CRC RAS mutant, MSS CRC RAS wildtype and HNSCC pretreated groups that show on-study decisions made under the model after the new groups are added (refer Protocol Section 14.4.4). The hypothetical data scenarios for interim and final analysis can be found in Protocol Table 14-16 and Protocol Table 14-17 respectively. For each scenario, the posterior probability of being “clinically meaningful” and “not clinically meaningful” (T1-T10 in Protocol Table 10-1) are calculated by group and displayed in the tables.

Similar exercise was conducted with the three additional tumor groups included in the protocol amendment 5 (i.e RCC IO naive, RCC IO pretreated patients and mCRPC, all treated at 240 mg BID dose of NIR178 in combination with PDR001) (refer Protocol Section 14.4.5). The hypothetical data scenarios for interim and final analysis can be found in Protocol Table 14-18 and Protocol Table 14-19 respectively.

3.2 Part 2

At least 20 patients will be enrolled in each of the dosing schedules.

[Table 3-1](#) shows the posterior mean and corresponding 90% credible interval for $N = 20$ (since it is planned to have approximately 20 patients in each schedule) for various observed ORR using a minimally informative unimodal beta prior distribution with parameters $a = 1/3$ and $b = 1$ (Note: this assumes a priori response rate of 25%). This is same for all dosing schedules.

Table 3-1 Posterior summaries for given number of responses (ORR)

Observed ORR (N, %)	Posterior mean (90% credible interval)	Probability of no improvement [0% - 20%]	Probability of limited improvement [20% - 33%]	Probability of clinically meaningful improvement [33%-100%]
0 (0%)	0.016 (0.00,0.070)	0.999	0.001	0.000
3 (15%)	0.156 (0.051, 0.299)	0.744	0.228	0.028
4 (20%)	0.203 (0.081, 0.356)	0.534	0.385	0.080
5 (25%)	0.250 (0.115, 0.414)	0.316	0.498	0.185
10 (50%)	0.484 (0.311, 0.657)	0.002	0.070	0.928
15 (75%)	0.718 (0.548, 0.863)	0	0	1
20 (100%)	0.954 (0.866,0.997)	0	0	1

From [Table 3-1](#), with a sample size of 20 patients, if the observed ORR is 25%, the probability of true ORR to be at least 33% is 18.5%. If the observed ORR is 50%, the probability of true ORR to be at least 33% is 92.8%. Also, with a sample size of 20, if the observed ORR is 15%, the probability of true ORR to be less than 20% is 74.4%.

[Table 3-2](#) shows the posterior probability that ORR for schedule 1 (S1) is greater than ORR for schedule 2 (S2) for various observed ORR using a minimally informative unimodal beta prior distribution with parameters $a = 1/3$ and $b = 1$. Similar approach can be used to compare schedule 2 to schedule 3 and schedule 1 to schedule 3.

Table 3-2 Posterior probability that schedule 1 (S1) has higher ORR than schedule 2 (S2)

Observed ORR in S1 (N, %)	Observed ORR in S2 (N, %)	Posterior mean of the difference (90% credible intervals)	Probability that ORR in S1 is greater than ORR in S2 given data
3 (15%)	0 (0%)	0.141 (0.027, 0.287)	0.981
4 (20%)	3 (15%)	0.046 (-0.142, 0.236)	0.660
5 (25%)	4 (20%)	0.047 (-0.160, 0.254)	0.646
5 (25%)	5 (25%)	0.000 (-0.213, 0.212)	0.499
10 (50%)	5 (25%)	0.234 (-0.001, 0.459)	0.949
10 (50%)	8 (40%)	0.095 (-0.152, 0.336)	0.740
15 (75%)	10 (50%)	0.235 (-0.003, 0.463)	0.948
15 (75%)	12 (60%)	0.140 (-0.094, 0.371)	0.839
20 (100%)	15 (75%)	0.235 (0.071, 0.414)	0.990

From [Table 3-2](#), with a sample size of 20 patients in each schedule, the posterior probability that ORR in S1 is greater than ORR in S2 is 50% if the difference between observed ORR in the two schedules is 0% respectively. However, if the difference between observed ORR in S1 and S2 is 5% respectively, the posterior probability that ORR in S1 is greater than ORR in S2 is approximately 65.0%. If the difference between observed ORR in S1 and S2 is 25% respectively, the posterior probability that ORR in S1 is greater than ORR in S2 is approximately 95.0%.

Table 3-3 **Posterior probability that schedule 1 (S1) has higher ORR than both schedule 2 (S2) and schedule 3 (S3)**

Observed ORR in S1 (N, %)	Observed ORR in S2 (N, %)	Observed ORR in S3 (N, %)	Probability that ORR in S1 is greater than ORR in S2 and S3 given data
3 (15%)	0 (0%)	0 (0%)	0.963
4 (20%)	3 (15%)	3 (15%)	0.509
5 (25%)	4 (20%)	3 (15%)	0.568
5 (25%)	5 (25%)	5 (25%)	0.335
10 (50%)	5 (25%)	5 (25%)	0.911
10 (50%)	8 (40%)	5 (25%)	0.719
15 (75%)	10 (50%)	10 (50%)	0.906
15 (75%)	12 (60%)	10 (50%)	0.814
20 (100%)	15 (75%)	12 (60%)	0.990

From [Table 3-3](#), with a sample size of 20 patients in each schedule, the posterior probability that ORR in S1 is greater than ORR in both S2 and S3 is 33.5% if the difference between observed ORR in the three schedules is 0% respectively. However, if the observed ORR in S1, S2 and S3 are 10%, 8% and 5% respectively, the posterior probability that ORR in S1 is greater than ORR in both S2 and S3 is 71.9%.

3.3 Part 3

If initiated, 20 patients will be enrolled in each group of treatment indication (max two) selected based on emerging data from Part 1 and Part 2. For the treatment indication/s selected in Part 3, appropriate intervals will be defined and specified before any reporting activity in the statistical analysis plan. Novartis may decide to not open Part 3 for enrollment based on emerging data from Part 1 and Part 2.

As of Protocol Amendment 6, 20-30 patients will enroll in TNBC indication using NIR178 160 mg BID continuous dosing schedule in combination with PDR001 (see [Section 1.1.3](#)).

A sample size of 10 patients treated at FCT NIR178 160 mg BID in combination with PDR001 in TNBC indication in Part 3 provides a high probability, 77%, of observing 0 or 1 adverse event when the true incidence rate is 9% ([Table 3-4](#)).

Table 3-4 **Probability of detecting adverse events with specified incidence rate based on N=10 patients**

Number of adverse events	AE incidence rate			
	0.05	0.09	0.12	0.15
0 or 1	0.91	0.77	0.66	0.54
2 or 3	0.09	0.22	0.32	0.41
>3	0.00	0.01	0.02	0.05

Regarding the efficacy of part 3, [Table 3-5](#) shows the posterior mean and corresponding 95% credible interval for N=20 for various observed ORR rates using a minimally informative unimodal beta prior distribution with parameters $a=0.176$ and $b=1$ for TNBC patients (Note: this assumes a priori response rate of 15%). From [Table 3-5](#), with a sample size of 20 patients, if the observed ORR rate is 15%, the probability of true ORR rate for TNBC patients to be at least 13% is 54.8%

Table 3-5 Posterior mean and 95% credible intervals for given ORR rates

ORR (N, %)	Posterior mean (95% credible interval)	Probability of no improvement [0% - 5%]	Probability of limited improvement (5%-13%)	Probability of clinically meaningful improvement [13%-100%]
0(0%)	0.008 (0.00,0.066)	0.958	0.038	0.004
2 (10%)	0.103 (0.015, 0.259)	0.220	0.495	0.285
3 (15%)	0.150 (0.036, 0.326)	0.060	0.392	0.548
4 (20%)	0.197 (0.062, 0.386)	0.012	0.217	0.771
5 (25%)	0.244 (0.091, 0.443)	0.002	0.092	0.906
10 (50%)	0.481 (0.277, 0.688)	0.000	0.000	1.000

Japanese safety run-in part

The period for evaluating DLTs will be cycle 1 (i.e. the first 28 days of treatment with single agent NIR178 or in combination with PDR001). The safety run-in will evaluate three NIR178 dose levels sequentially. Each dose level may consist of 3 to 6 newly enrolled patients who have tumor histologies specified in Protocol Section 5, and who meet all other inclusion/exclusion criteria. The dose escalation strategy is detailed in [Section 1.1.4](#).

4 Change to protocol specified analyses

The study is closed out due to lack of sufficient efficacy and there is only TNBC indication opened in Part 3 at a single dose level - NIR178 160 mg BID. The dose increment criteria of Part 3 described in Section 1.1.3 will not be evaluated as no patients are enrolled at 240mg in Part 3.

5 Appendix

